#### Drug Availability IND Exempt (IND #122334)

**Supplied Investigational Agents:** Placebo for metformin supplied and compounded by Pharm Ops, Inc., in Phillipsburg, NJ.

Commercial Agents: Metformin will be purchased through the McKesson Clinical Research Services.

#### Alliance A211102

- \* Placebo is discontinued; however, assessments continue per protocol.
- 1 For patients undergoing initial RPFNA at surgery, only the unaffected/non-operated breast should be aspirated. This applies to patients undergoing surgery for DCIS and/or any atypical lesions. Only the contralateral breast can be aspirated in patients with DCIS. Aspiration of the unaffected breast is at the discretion of the subject's treating surgeon.
- 2 Only the breast(s) originally aspirated prior to randomization will undergo follow-up RPFNA.
- 3 Follow up visits will be performed at 36 and 48 months after the start of treatment.

Serum and whole blood samples for mandatory correlative science studies will be collected prior to treatment, and at 6, 12, and 24 months (see Section 14.0).

Site RPFNA Credentialing: Sites must either have been previously approved for participation in CALGB 70806 or routinely perform RPFNA (> 10 RPFNA per year); OR undergo RPFNA training (see Section 6.2.5).

#### 1.0 BACKGROUND

#### 1.1 Background

There is a need for alternative prevention strategies with acceptable toxicities. Tamoxifen (Tam) is currently standard of care for breast cancer prevention in women with atypia. While there are clear benefits to Tam, Tam does not prevent estrogen receptor-negative (ER-) breast cancer and only prevents half of ER (+) breast cancer. Additional interventions are needed to prevent ER (-) breast cancer.

We have performed over 3,000 RPFNA and have not found a RPFNA that was suspicious for cancer (unless we already knew that the woman was being evaluated via a surgical work up for suspected cancer). We include a detailed description of information that is communicated to women undergoing RPFNA regarding their cytology results (see Section 14.6.1.2). Women are told that this RPFNA is an investigational protocol. If findings are found that are suspicious for cancer the woman will have a clinical breast examination, mammogram, and, if clinically appropriate, breast magnetic resonance imaging.

#### 1.2 Rationale

### 1.2.1 Evidence for Metformin from Population and Clinical Studies

Metformin (1,1-dimethylbiguanide hydrochloride) is a well-tolerated biguanide currently undergoing testing for secondary breast cancer prevention in women with prior breast cancer. Metformin belongs to a biguanide class of oral hypoglycemic agents and prescribed to over 120 million Type II diabetic patients worldwide, with an excellent safety profile. Recently published population studies suggest that metformin decreases the incidence of cancer and cancer-related mortality in diabetic patients. Other clinical and epidemiologic evidence links hyperinsulinemia and insulin resistance to increased mitogenic effects and thus to increased risk of several cancers, in addition to leading to poor breast cancer outcomes. In addition, it is also hypothesized that insulin can promote tumorigenesis via a direct effect on epithelial tissues, or indirectly by affecting the levels of other modulators, such as insulin-like growth factors, sex hormones, and adipokines. In a limited retrospective study of patients who received neoadjuvant chemotherapy for breast cancer showed that diabetic cancer patients receiving metformin during neoadjuvant chemotherapy had a higher pathological complete response rate than diabetic patients not receiving metformin (24% versus 8%, p = 0.007) providing evidence for the potential role of metformin as an antineoplastic agent for breast cancer.

#### 1.2.2 Evidence for Metformin from in vitro and preclinical studies

The antineoplastic effects of metformin in breast cancer are supported by its modulation of signaling keynodes associated with breast cancer. Several lines of evidence demonstrate that metformin inhibits the growth of tumor cells, including breast cancer cells. In the liver, Metformin inhibits transcription of key gluconeogenesis genes and increases glucose uptake in skeletal muscle. It reduces levels of circulating glucose, increases insulin sensitivity, and reduces insulin resistance-associated hyperinsulinemia. There is evidence that metformin exerts its anti-diabetic effects through inhibition of complex 1 of the mitochondrial respiratory chain. At the level of cell signaling, several mechanisms of metformin action have been proposed; the most important one relates to the activation of AMPK. Metformin regulates the AMPK/mTOR pathway. Work by Zakikhani, et al. demonstrated that Metformin inhibits the growth of breast cancer cells in an AMPK-dependent manner. Several tumor suppressors are involved in the AMPK signaling network and activated AMPK results in suppression of cell proliferation in normal and tumor cells. The growth

inhibition was associated with decreased mTOR activation and a general decrease in mRNA translation. Given the potential complexity of metformin, it is important to design biomarkers to evaluate the full range of metformin's downstream signaling targets.

#### **1.3 Feasibility and Preliminary Studies**

#### 1.3.1 Random Periareolar Fine Needle Aspiration (RPFNA)

RPFNA is a research technique developed to test for early cytological changes in women who are at high-risk for developing breast cancer. RPFNA has been prospectively validated in high-risk women to test for 1) short-term breast cancer risk and 2) response to chemoprevention. The presence of atypia in RPFNA predicts a 5-6-fold independent increase in breast cancer risk in high-risk women. These observations support the use of cellular atypia in RPFNA as an independent surrogate marker of short-term breast cancer risk in high-risk women.

#### **1.3.2 CALGB RPFNA Study**

There is increasing acceptance of RPFNA. The Cancer and Leukemia Group B (CALGB) Prevention Group tested the reproducibility of RPFNA in a multi-institutional crosssectional study. Sixty-three high-risk women from five CALGB institutions (Duke, Ohio State, Roswell Park, Dana Farber, and Vermont) underwent RPFNA. Duplicate bilateral RPFNA was performed on each woman by a single investigator on a single day. Masood Cytology Index score was assessed by a single blinded cytopathologist. We observed a high degree of statistical agreement in the Masood Cytology Index scores of duplicate RPFNA samples from the same breast, with a Spearman correlation coefficient of 0.8312 (p<0.0001). Our multi-institutional study demonstrates that RPFNA is a reproducible measure of breast cytology in a cooperative group cross-sectional trial. RPFNA did not demonstrate a high degree of agreement between breasts, suggesting that breast cancer risk and progression may occur at different rates in individual breasts from a single woman. These studies provide proof-of-principle for future RPFNA-based studies.

#### **1.3.3 RPFNA and Response to Tam Prevention**

In a single institution Pilot and Feasibility analysis at Duke University we tested for persistent atypia in a heterogeneous collection of 40 high-risk women who took Tam prevention. Women underwent RPFNA before and after Tam chemoprevention administered at 20 mg/day. The presence or absence of atypia was measured by a single blinded cytopathologist using a 1) five point qualitative descriptor (normal, hyperplasia, atypia, suspicious, cancer) and 2) a numeric scoring system, the Masood Cytology Score Index. After 12 months of Tam, approximately half of the women had persistent cytological atypia in their RPFNA aspirate and half had disappearance of cytological atypia. RPFNA was performed at 18 and 24 months; no woman who had persistent atypia at 12 months had disappearance of atypia at 18 and 24 months.

#### 1.3.4 High Through-Put Reverse Phase Protein Microarray of RPFNA

Reverse Phase Protein Microarray (RPPM) profiling of RPFNA cytology is able to detect protein phosphorylation patterning in 10,000 micro-dissected epithelial cells. In our published studies, RPPM profiling of RPFNA cytology was tested in 5,000 micro dissected epithelial cells in duplicate. Each array was scanned; spot intensity was analyzed; data were normalized; and a standardized, single data value was generated for each sample on the array (Image Quant v5.2). Spot intensity was integrated over a fixed area. Local area background intensity was calculated for each spot with the unprinted adjacent slide background.

#### 1.3.5 RPPM analysis of RPFNA cytology

In a single institution study at Duke University, we tested for the reproducibility of RPPM measurements for 53 individual proteins in quadruplicate. RPFNA samples from two independent test sets of 38 and 39 high-risk women. Importantly, there was a high level of community participation in this trial. Of the 77 women enrolled in this trial, 45% (35/77) of women in this trial were African American. Five thousand epithelial cells were Microdissected, solubilized, and tested by RPPM. Duplicate samples were prepared from micro dissection of paired RPFNA aspirates. Fifty of 53 proteins tested by RPPM had an interclass correlation coefficient of agreement of >0.80. These 50 proteins included EGFR, EGFR-pTyr992, EGFR-pTyr1148, ErbB2, ErbB2-pTyr1248, ErbB3, ErbB3-pTyr1289, IGF1R, ER $\alpha$ , ER $\alpha$ -pSer118, IRS1-pSer612, MEK-pSer217/221, ERK-pThr202/Tyr204, HIF1 $\alpha$ , VEGF, GSK3 $\beta$ , AKT-pSer473, mTOR-Ser2448, 4EBP1-pThr37/46, eIF4G-pSer209, 70S6K-pThr412, FKHR-pSer256, IKB-pSer32-36, NF $\kappa$ B(p65)-pSer536, Bad-pSer136, Bcl2-pSer70, 14-3-3- $\zeta$ , p38MAPK, p90RSK, PTEN-pSer380, p53, p21, Stat3, Stat5, Src-pTyr416, Fak-pTyr576, paxillin,  $\beta$ catenin-pThr42/Ser41, Snail-1, vimentin, E-cadherin, pACC-pSer79, and IRS1-pSer612.

**Three high-intensity ER(-) clusters were identified: 1) Cluster #1** activated Akt/mTOR/insulin/Stat3/vimentin: AKTpSer473, mTORpSer2448, 4EBP1pThr37/46, eIF4GpSer209, 70S6KpThr412, p38MAPK, p90RSK, 14-3-3, Src-pTyr416, Fak-pTyr576, Stat3-pTyr694, Stat3-pSer727, vimentin, ACC-pSer79, and IRS1-pSer612. 2) Cluster #2 activated EGFR/MEK/ERK:EGFR, EGFRpTyr1068, MEKpSer217/221, ERKpThr202/Tyr204, HIF1α, VEGF, GSK3β-pTyr279/216, βcatenin-pThr42/Ser41. **3) Cluster #3** mitochondrial survival proteins Bad, Bad-pSer137, Bcl2-pSer270, Bax, Bcl-xl, PTEN-Ser137.

These data demonstrate our ability to test for phosphoprotein expression in mammary cytology from high-risk women. We also provide evidence for our ability to recruit African American women to RPFNA trials. The ability to associate RPFNA cytology with RPPM in a longitudinal study will lead to increased understanding of signaling pathways activated during breast cancer initiation.

#### 1.3.6 Rationale for Metformin Dose

Our rationale for dose selection was to maximize bioavailability and the opportunity to observe efficacy for this new indication, while minimizing toxicity and adverse events in this cohort, based on earlier studies where metformin was used in other indications and age groups.

There is evidence that the use of metformin in individuals with "normal" insulin levels appears to be safe and it reduces insulin levels. Studies by Goodwin *et al.* show that in breast cancer patients given metformin (1500 mg/day), the mean baseline fasting insulin level was in the "normal" range (75.7 pmol/L) and only one woman had an insulin level above 140 pmol/L (the level was 150 pmol/L). Insulin levels were reduced by 22% without the occurrence of hypoglycemia. Similar safety and insulin-lowering effects of metformin have been reported in non-diabetic, non-breast cancer subjects with normal insulin levels.

In a recent study of polycystic ovary syndrome (PCOS), metformin (2250 mg/day) lowered fasting insulin levels by 18% from a mean baseline insulin of 64.5 pmol/L in women in the lowest quartile of baseline insulin (greater reductions were seen in women with insulin levels markedly above normal). Similar results in PCOS subjects were reported by Roumaldi (mean baseline fasting insulin 47.0 pmol/L, 15% reduction after metformin at a low dose of 1000 mg/day for 6 months). Based on these observations, we anticipate that metformin will safely lower insulin levels but not promote significant hypoglycemia.

There is clinical evidence that fasting insulin levels are associated with poor breast cancer outcomes. We have chosen a dose of metformin for breast cancer prevention that mirrors MA-32, an ongoing adjuvant multicenter trial of metformin vs. placebo in women with breast cancer. At the dose we propose Metformin safely lowers insulin levels by about 20% in 1) non-diabetic women with breast cancer and 2) women without cancer who have baseline fasting insulin levels in the normal range. Evidence in observational, non-interventional trials suggests that metformin use in diabetics may reduce cancer risk and mortality in women receiving chemotherapy for breast cancer. We hypothesize that the dose of metformin we propose will reduce breast cancer risk through its secondary targeting of insulin/Complex 1 and primary targeting of AMPK/Akt/mTOR.

There is growing evidence that metformin exerts an insulin independent effect on breast cancer via activation of an insulin independent 1) AMPK-dependent energy stress response and 2) PI3K/Akt/mTOR. The existence of this direct (non-insulin dependent) metformin's effect on AMPK/mTOR^14 provides justification for inclusion of women with a broad range of insulin levels in rather than limiting enrolment to those with insulin levels above an arbitrarily chosen cut-point. Because metformin is a readily available, inexpensive oral agent, with known (and easily manageable) toxicities, we believe evaluation of its ability to prevent breast cancer will be feasible as well as tolerated.

#### 1.3.7 Summary of Feasibility Data and Significance

Ultimately, the most effective way to reduce breast cancer mortality is to prevent breast cancer. Here we aim to conduct prevention trials using biomarker-guided efficacy evaluation with an agent that targets signaling pathway that is known to be activated in ER-breast cancer. Metformin is a well-tolerated, inexpensive, oral hypoglycemic agent and prescribed to over 120 million Type II diabetic patients worldwide, and is safe in pregnancy. While metformin is undergoing pilot clinical testing in women with breast cancer, metformin's mechanism of action is poorly understood. It is known that metformin targets Akt/mTor, AMPK, and promotes a secondary reduction in mitochondrial complex 1 and insulin signaling. However, there is also evidence that metformin may also target NF $\kappa$ B and IL6. Given the potential complexity of metformin, we need to be able to precisely track signaling pathways targeted by metformin prevention.

We have developed the scientific framework, biomarkers, and strategies to test the ability of targeted agents to eliminate cytologic atypia in high-risk women. Using our combined proteomic/tracking tools we can directly test in an individual woman 1) for activated signaling pathways, 2) whether the prevention agent eliminates cytologic atypia, and 3) if not, we can then identify additional signaling pathways that can be targeted. The ability to test whether a prevention drug is working in an individual woman allows us to rapidly deliver targeted prevention tailored to an individual woman.

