#### 2.2 Secondary objectives

- **2.2.1** Use the Masood Cytology Index Score to test for the presence of cytological atypia or disappearance of cytological atypia in RPFNA aspirates after 12 months for both arms, and 24 months (24 month is optional for placebo-only group for patients who remain on placebo arm and will not receive metformin, and mandatory for crossover patients) for women receiving metformin 850 mg p.o. bid (metformin group).
- **2.2.2** Compare Masood Cytology Score values at 0 and 12 months in right and left breasts (if both breasts were aspirated) from the same individual in the metformin and placebo group.
- **2.2.3** Test the reproducibility of RPPM in duplicate RPPM determinations from individual RPFNA specimens.
- **2.2.4** Correlate baseline RPPM values with presence of atypia (as measured by Masood Cytology Index Score) at month 12 and month 24 (month 24 optional for placebo-only group; for patients who remain on placebo arm and will not receive metformin) RPFNA.

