#### **16.0 STATISTICAL CONSIDERATIONS AND METHODOLOGY**

#### 16.1 Study Design

#### **16.1.1 Study Populations**

A total of 177 premenopausal women will be pre-registered, among which 96 patients with atypia (Masood Score 14-17) on RPFNA at baseline are expected to be randomized between

Metformin arm and placebo control arm. It is expected that the accrual rate will be 1 patient per month and that accrual will be completed about 8 years after study activation. The randomization will be stratified for known BRCA mutation (BRCA1 or BRCA2 mutation vs. no mutation), prior excisional biopsy (atypical epithelial hyperplasia, atypical lobular hyperplasia, flat epithelial hyperplasia vs. DCIS vs. LCIS), and baseline fasting insulin > 2x ULN vs.  $\leq 2x$  ULN.

At 12 months the women in the placebo arm will be allowed to take metformin. Based on experience from 300 women undergoing serial RPFNA at Duke, it is anticipated that approximately 40% of women who are randomized to the metformin arm will have disappearance of atypia at 12 months and 60% will have persistent atypia. The estimated drop-out rate is 5% at 6 months and 10% at 12 months. Over 98% of women with atypia will have atypia on repeat RPFNA on the non-metformin arm.

We propose to test RPFNA on both right and left breasts at, 12 and 24 months after registration/randomization for the presence or absence (Masood score  $\leq$ 13) of atypia by Masood Cytology Index Score. The RPFNA at 24 months is optional for women who continue on the placebo control arm and will not receive metformin. The outcomes collected at 24 months will be exploratory. In analysis, we will consider taking a transformation, such as logarithm, of positive variables in order to improve the normality and variance stabilization. Among the 96 randomized patients, we expect that about 10% of patients will drop out at month 12. So, the power analyses are based on N= 88 patients (44 per arm).

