#### **16.2.1.1 Primary Analysis**

Multiple Masood scores from each breast will be averaged for each time point. The primary endpoint of the study is the binary outcome of atypia (Masood score  $\geq$  14). In this analysis, the sampling units will be women, so that, if a woman has atypia in one breast and no atypia in the other breast, this woman will be called atypia. Presence of atypia at month 12 will be compared between two arms using the chi-square test in univariate analysis, and regressed on group indicator, age, race, stratification factors, and baseline Masood score using logistic regression in multivariate analysis. As an exploratory analysis, we will also conduct a regression analysis including the timing of baseline RPFNA (intraoperative vs. in clinic) and the number of breasts with atypia at baseline in addition to these covariates. With 44 women per arm, the primary analysis has 90% of power to detect a difference of 90% vs. 60% of atypia between placebo and metformin arms at month 12 by a chi-square test with alpha=5%.

In order to address the worst score rule, we will repeat above analyses using the maximum, instead of average, Masood score from each breast.

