# 16.2.2.4 Correlate baseline RPPM values with presence of atypia at month 12 and month 24:

We will combine data set of metformin and no-metformin groups (N = 88) and use the breasts as the sampling units in this analysis. The possible dependency in observations between the left and right breasts for each woman will be adjusted using the GEE approach.

The baseline RPPM value of each protein will be correlated with Masood cytology score at month 12 using a simple linear regression method. In a multivariate analysis, Masood score at month 12 will be regressed on the baseline RPPM value of each protein, group indicator, age, race, prior excisional biopsy, and baseline Masood scores. Similar analysis will be conducted using the change rate of Masood score between baseline and month 12 in place of Masood score at month 12.

The baseline RPPM value of each protein will be correlated with presence and absence of atypia at month 12. A total of 50 proteins will be tested, so that the significance of each protein will be adjusted for multiple testing by controlling the family-wise error rate (FWER) using the permutation method. We expect that about 60% of the women will have persistent atypia at 12 months. The 50 proteins were selected from a previous study so that they are expected to have reasonable effect sizes. Assuming that each woman contributes samples from only one breast and the proteins have correlation coefficient of 0.1, the multiple testing procedure controlling the FWER at 10% level by two-sided tests will have about 90% probability to detect 15 or more proteins if 25 of the 50 proteins have an effect size of 0.8 times SD [Jung and Young, 2011]. Since about 75% of women are expected to contribute samples from both breasts to the study, the real power for this analysis will be higher.

In a multivariate analysis, presence of atypia at month 12 will be regressed on the baseline RPPM value of each protein, group indicator, age, race, prior excisional biopsy, and baseline Masood scores.

A similar analysis will be conducted to correlate baseline RPPM value of each protein with Masood score and presence/absence of atypia at month 24.

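### The family-wise-controlled protein screen in Section 16.2.2.4 pools the arms with no arm term, which dilutes markers of metformin non-response and leaves them indistinguishable from markers of persistence in general

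*Combined protocol and SAP*

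**What the plan says.** Secondary objective 2.2.4 is to "Correlate baseline RPPM values with presence of atypia (as measured by Masood Cytology Index Score) at month 12 and month 24". Section 16.2.2.4 carries it out: "We will combine data set of metformin and no-metformin groups (N = 88"). For the binary outcome, "The baseline RPPM value of each protein will be correlated with presence and absence of atypia at month 12", over 50 proteins, with the family-wise error rate held at 10% by permutation. No arm term or stratification by arm is described for this screen. A separate multivariate model for atypia includes the group indicator and other covariates. No error control is stated for that model, and neither a protein-by-arm term nor an arm-specific estimate is listed.

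Elsewhere the plan expects the arms to differ greatly on this outcome. The primary analysis (Section 16.2.1.1) is powered for a "difference of 90% vs. 60% of atypia between placebo and metformin arms at month 12". Section 16.1.1 anticipates that 40% of "women who are randomized to the metformin arm will have disappearance of atypia at 12 months and 60% will have persistent atypia", and also states: "Over 98% of women with atypia will have atypia on repeat RPFNA on the non-metformin arm".

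The background in Section 1.3.7 says that the proteomic and tracking tools can test, in an individual woman, "whether the prevention agent eliminates cytologic atypia, and 3) if not, we can then identify additional signaling pathways that can be targeted".

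**The concern.** When two arms with very different persistence rates are combined without an arm term, the persistent group is mostly placebo women and the cleared group is mostly metformin women. Two things follow.

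- **Dilution.** Randomisation makes the expected baseline protein level equal in the two arms. The part of the outcome contrast that is simply metformin against placebo therefore carries no protein signal. It only weakens a real within-arm association.
- **Interpretation.** A flagged protein may mark women in whom metformin does not clear atypia, or women whose atypia persists whatever they take. With no arm-specific estimate, the output does not say which. A general marker of persistence could then be reported as a pathway to target when metformin fails.

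**Working it through.** **Inputs.** 44 evaluable women per arm (Section 16.1.1: "the power analyses are based on N= 88 patients (44 per arm")); persistence 60% on metformin and 90% (16.2.1.1) or 98% (16.1.1) on placebo; effect 0.8 SD, 50 proteins and family-wise error 10% (16.2.2.4). Assumptions: the 0.8 SD applies within arm, each woman gives one breast (the plan's own simplification for power), and p<0.002 (0.10/50) stands in for the permutation threshold.

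**The plan's own figure.** Section 16.2.2.4 states about 90% probability of detecting 15 or more of 25 true proteins. With 88 women split 60/40 and correlation 0.1, simulation with max-T control gives 90.3% (step-down, normal approximation); single-step variants with the same common correlation give 80% to 86%. So the stated figure can be reproduced, but only with 60% persistence in the pooled sample. The arm rates above imply (90+60)/2 = 75% or (98+60)/2 = 79%.

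**Make-up of the groups at month 12.**

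| | Placebo 90% | Placebo 98% |
|---|---|---|
| Persistent: metformin + placebo | 26.4 + 39.6 = 66.0 | 26.4 + 43.1 = 69.5 |
| Placebo share of persistent | 39.6/66.0 = 60% | 43.1/69.5 = 62% |
| Cleared: metformin + placebo | 17.6 + 4.4 = 22.0 | 17.6 + 0.9 = 18.5 |
| Metformin share of cleared | 17.6/22.0 = 80% | 17.6/18.5 = 95% |

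**Dilution.** Within an arm the information on a persistent-against-cleared difference is 44p(1−p). On metformin this is 44×0.6×0.4 = 10.56; on placebo it is 3.96 (90%) or 0.86 (98%). The within-arm total is 14.52 or 11.42. The pooled test uses n1×n2/88 = 66×22/88 = 16.50, or 69.52×18.48/88 = 14.60. The excess, 1.98 or 3.18, is the between-arm part, which has no protein signal in expectation. So:

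- pooled difference = 0.8 × (information from arms where the link exists) / (pooled information)
- pooled expected z = that difference × √(pooled information)
- arm-stratified expected z = 0.8 × (information from arms where the link exists) / √(within-arm total)

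| Protein | Pooled difference, SD (90% / 98%) | Pooled z | Stratified z |
|---|---|---|---|
| Linked on metformin only | 0.51 / 0.58 | 2.08 / 2.21 | 2.22 / 2.50 |
| Linked in both arms (prognostic) | 0.70 / 0.63 | 2.86 / 2.39 | 3.05 / 2.70 |
| Linked on placebo only | 0.19 / 0.05 | 0.78 / 0.18 | – |

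In the metformin arm alone, a 0.8 SD link gives z = 0.8×√10.56 = 2.60.

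**Power at p<0.002** (simulated, t statistics, equal expected baseline means in the two arms):

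| Protein | Pooled (90% / 98%) | Stratified by arm (90% / 98%) | Metformin arm alone |
|---|---|---|---|
| Linked on metformin only | about 13% / 16% | about 17% / 25% | about 25% |
| Prognostic | about 37% / 22% | about 44% / 32% | about 25% |

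**Can the two kinds be separated?** A metformin-only screen finds both kinds equally often, so separation needs the placebo estimate as well. That estimate rests on 44×0.10 = 4.4 or 44×0.02 = 0.9 placebo clearers. The standard error of a protein-by-arm difference is √(1/10.56 + 1/3.96) = 0.59 SD, or √(1/10.56 + 1/0.86) = 1.12 SD.

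**The case against.** The strongest reply is that Section 16.2.2.4 does what objective 2.2.4 asks. The objective is association with atypia and is not restricted to women in whom metformin failed. A reader might infer from Section 1.3.7 that the pooled screen is the step meant to identify what to target after metformin failure. The documents do not say so: the sentence is background on what the tools can do in an individual woman, and it does not refer to this analysis. This stands, and it is why the point rests on 16.2.2.4.

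Second, an arm-adjusted model is already planned. With arm as a main effect, power for a metformin-specific protein is about 16% (placebo 90%) or 25% (98%), so at 98% little is lost against the metformin arm alone. This is fair, but it applies to the multivariate model. The screen with family-wise control, on which detection and the power claim rest, has no arm term. A main effect also cannot show whether a protein's association differs between arms.

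Third, the trial is too small to do much better. A metformin-only screen of 44 women has about a 2% to 8% chance of 15 or more detections, and interaction estimates depend on about 1 to 4 placebo clearers. This stands too. It argues for an exploratory label on those outputs, not for leaving them out.

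**Conclusion.** The point holds as one of dilution and of failure to separate two kinds of protein. At the plan's rates, 60% to 62% of the month-12 persistent group are placebo women. A 0.8 SD metformin-specific link appears as about 0.51 to 0.58 SD, and its power at p<0.002 is about 13% to 16% pooled against about 25% in the metformin arm alone. Because about 75% of women are expected to give two breasts, all the powers would be somewhat higher in practice.

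Three stronger readings are not supported.

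- A reader might infer that pooling favours proteins unrelated to metformin response. It does not: 80% to 95% of cleared women took metformin, and a protein linked to clearing only on placebo appears at 0.19 SD or less.
- A reader might infer that prognostic proteins swamp metformin-specific ones. With baseline means equal across arms, as randomisation implies, detection is about 37% against 13% at 90% placebo persistence, but only about 22% against 16% at 98%. A prognostic protein also separates clearers from non-clearers on metformin.
- A reader might infer that the placebo women counted here never took metformin. That is true only at month 12; Section 7.3 lets them cross over afterwards, and the objective also covers month 24.

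**What to change.** In Section 16.2.2.4:

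1. Stratify the family-wise-controlled screen by arm, using an arm-adjusted statistic for each protein and permuting within arm. Label the result as association with persistence in general. On the figures above this raises power for both kinds of protein.
2. Report each protein's metformin-arm and placebo-arm estimates with confidence intervals, together with a protein-by-arm term, all labelled exploratory.
3. Restate the power sentence for the stratified statistic, and say that a metformin-only screen of 44 women has little power.

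The cost is SAP wording and a few more model runs on data already collected. The limitation is that, with about 1 to 4 placebo clearers, the interaction estimates will be wide and will rarely settle whether a given protein is specific to metformin.
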